9.2.4 Baseline Period

This is a cross-sectional survey that does not involve any follow-up of patients and caregivers. Eligibility criteria will be assessed and patient/caregiver questionnaire completed at one point in time within the data collection period.

9.3 Variables

The questionnaire will contain multiple-choice questions with no free text fields.

The patient/caregiver questionnaire will be structured as follows:

- A. Acceptance to participate (Informed consent: date and signature **as required**)
- B. Screening: eligibility, demographics
- C. Main questionnaire domains

Section B (Screening) will collect socio-demographic characteristics (age, gender, educational status) about patients/caregivers. The questionnaire will be designed to take a maximum of 10-15 minutes to complete.

The questionnaire will assess the following key concepts related to the patient/caregiver card and brochure:

- Receipt of the patient/caregiver brochure and card.
- Knowledge about key information in the patient/caregiver brochure.
- Behaviours outlined in the patient/caregiver brochure and card.
- Usage of the patient/caregiver brochure and card i.e. whether the patient card is filled in with the required information, whether the patient card is shown to healthcare providers while on treatment with Blincyto, whether patients/caregivers read and refer to the educational materials and reasons for not reading them.
- Understanding of the patient/caregiver brochure and card.

9.3.1 Exposure Assessment

Patients included in the study will **have been exposed to blincyto: they will be asked about their experience of Blincyto educational materials. Questionnaires may be completed at first exposure or following first exposure (Figure 2)** . Caregivers of patients meeting the selection criteria will also be invited to participate.

9.3.2 Outcome Assessment

The primary endpoints for the patient/caregiver survey are:

- Receipt: A categorical variable will describe if patients and caregivers received the brochure and/or card.
- Knowledge: A mean score will be created to summarise individual patient and caregiver scores. An individual patient/caregiver score is calculated as the proportion of all knowledge questions with correct responses.

The secondary endpoints for the patient/caregiver survey are:

- Behaviour: A mean score will be created to summarise individual patient and caregiver scores. An individual patient/caregiver score is calculated as the proportion of all behaviour questions with correct responses.

- **Understanding:** Among patient and caregivers who have read the patient/caregiver brochure and card, an ordinal scale will describe the self-reported level of understanding.
- **Usage:** A mean score will be created to summarise individual patient and caregiver scores. An individual patient/caregiver score is calculated as the sum of the 'value' of responses to all usage questions (ordinal scale) divided by the maximum possible score. Among patients and caregivers who have not read the materials, a categorical variable will describe the reasons for not reading them.

9.3.3 Covariate Assessment

The following sociodemographic characteristics will be collected and used to describe the sample:

- Country
- Age group (<65 years; >65 years)
- Gender (male/female)
- Respondent type (patient/caregiver)
- Educational level (categories vary by country)
- Number of days on Blincyto

9.3.4 Validity and Reliability

Qualitative techniques will be used to ensure that the patient/caregiver questionnaire is readable, understandable and easy-to-use.

The questionnaire will be developed in English and conceptually reviewed by 5 haematology non-ALL patients (and not treated with Blincyto) and/or caregivers in the UK. The questionnaire will be subsequently translated and linguistically validated with 3 patients/caregivers in each of the participating countries. ALL patients will not be used to validate the questionnaire so that the recruitment for the survey is not affected.

During the linguistic validation interviews, trained interviewers will ask participants to complete the questionnaire while 'thinking aloud' and to describe their thinking and thought processes as they answer each question, each section and the questionnaire as a whole. The results will be used to optimize instructions, guidance, wording, response choices, as well as language.

A master version of the questionnaire will be generated following linguistic validation in the participating countries.

9.4 Data Sources

Data for this survey will be collected by means of a questionnaire developed for patients and their caregivers. In view of the severity of the disease, responses will be collected through a paper questionnaire in the clinic.

The questionnaire will be developed following standard survey principles. It will mainly include multiple choice questions with no free text fields.

In addition to the paper questionnaire, an identification log will be completed by the study site. The feasibility and recruitment process will be registered in an excel database.

9.5 Study Size

Based on precision calculations provided in Table 2, the survey aims to recruit approximately [CCI] patients and/or their associated caregivers to allow precisions of [CCI] [redacted] for correct responses of 60% and 90%, respectively, for the primary endpoint question of receipt. For the score of correct responses to knowledge questions ranging from 0 to 10 (

Table 3), a sample size of [CCI] patients and [CCI] caregivers would produce two-sided 95% confidence intervals with a distance from the mean to the confidence limits ranging from [CCI] [redacted] when the estimated standard deviation ranges from [CCI] [redacted] respectively.

These confidence intervals are wider than generally used, however, considering the orphan indication for Blincyto, severity of disease and variable patient well-being during treatment that may limit the number of patients available to participate in the study, this sample size is considered feasible and also appropriate to address the study objectives. It is to be noted that the final survey sample size will depend on patients/caregivers' willingness to participate in the survey within the study period.

Table 2. Precision of survey for [CCI] patients and caregivers according to a range of correct response to the primary endpoint question of receipt using the Clopper-Pearson method

Sample size	Correct Response	95% Lower Confidence Limit	95% Upper Confidence Limit
[CCI]	60%	[CCI]	[redacted]
	70%	[redacted]	[redacted]
	80%	[redacted]	[redacted]
	90%	[redacted]	[redacted]
	60%	[redacted]	[redacted]

Sample size	Correct Response	95% Lower Confidence Limit	95% Upper Confidence Limit
CCI	70%	CCI	CCI
	80%		
	90%		
	60%		
	70%		
	80%		
	90%		
	60%		
	70%		
	80%		
	90%		
	60%		
	70%		
	80%		
	90%		

Table 3. Precision of survey for CCI patients and caregivers according to assumed standard deviations for the mean score of a range of correct responses to the primary endpoint questions of knowledge using the Clopper-Pearson method

Sample size	Expected SD around the mean score of correct responses	Precision (distance from mean to limits)
CCI	0.5	CCI
	1.5	
	0.5	
	1.5	
	2.5	
	3.5	
	0.5	
	1.5	
	2.5	
	3.5	
	0.5	
	1.5	
	2.5	
	3.5	
	0.5	

Sample size	Expected SD around the mean score of correct responses	Precision (distance from mean to limits)
CCI	1.5	CCI
	2.5	
	3.5	
	0.5	
	1.5	
	2.5	
	3.5	

Approximately CCI patients and CCI caregivers will be recruited from approximately CCI units across all participating countries in proportion to the volume of patients with R/R Ph- ALL in each country; usage of Blincyto will be unknown in some countries and only estimated at the initiation of launch.

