The information in this document cannot be used for any purpose other than the evaluation or conduct of the research without the prior written consent of Amgen Inc.

If you have questions regarding how this document may be used or shared, call CCI
Amgen's general number in the US ([name]).

Investigator's Agreement

I have read the attached protocol entitled 'A cross-sectional survey of patients and caregivers receiving Blincyto in routine clinical practice in Europe to evaluate the effectiveness of additional risk minimisation measures', dated 06 November 2016, and agree to abide by all provisions set forth therein.

I agree to ensure that the confidential information contained in this document will not be used for any purpose other than the evaluation or conduct of the clinical investigation without the prior written consent of Amgen Inc.

Signature

Name of Investigator

Date (DD Month YYYY)

Study Design Schema

Questionnaire development and testing

The patient/caregiver questionnaire will be developed in English. This questionnaire will be first reviewed by 5 haemato-oncology non-ALL patients not treated with Blincyto and caregivers in the UK and will be later translated and linguistically validated with 3 patients/caregivers in each of the participating countries.

Identify haematology centres where Blincyto is or may be prescribed

Amgen's country affiliates will work with CCI to identify centres where Blincyto is prescribed or may be prescribed. A sampling list will be created. All centres/identified haemato-oncologists in this list will be approached. A qualification assessment will be performed to identify those centres/haematologists who are eligible and willing to participate. A total of approximately 10 haematology centers will be selected to participate in the study

Selection of patients and caregivers

Patients and their caregivers will be selected by the centre's haemato-oncologists/nurses in a consecutive manner based on the date of initiation of treatment with Blincyto. Sites will be asked to keep a log of anonymized demographic profiles (age and sex) of all patients administered Blincyto and their caregivers.

Survey data collection

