Only patients/caregivers able to understand and complete the informed consent and questionnaire will be included in the survey. Efforts will be made to write the questions in such a way that they can be readily understood by patients/caregivers with different educational levels so that ineligibility and inaccurate or missing responses for this reason are kept to a minimum. Non-response of items should be minimized due to the rigorous process of questionnaire development, validation and testing.

Patients/caregivers' responses may be biased if they are allowed to refer to the aRMM educational brochure and patient card. As a result, this would be minimized by explaining that responses should be based on assessing what they currently know and that they should not refer to the materials. At the time of completing the questionnaire, in the hospital clinic setting keeping materials out of reach should be readily feasible.

Self-reporting of actions and behavior may be biased towards positive values. The development of a questionnaire carefully pre-tested before actual study starts aims to minimize such a bias.

Recall bias is an inherent limitation of questions asking about the past. However, in this situation where **cycles** of therapy **are** administered over a short period of time (28 days **each**), this should be minimal.

The conduct of the survey may cause centres to provide more information to patients and caregivers. This 'Hawthorne' effect will be minimized by training sites to provide limited information about the survey in communications with the patients/caregivers.

The size of the study populations will allow an acceptable level of precision (considering the rarity of the disease) for each strata (patients and caregivers) for the study primary endpoints. Subgroup analyses will be exploratory and limited due to the small number of patients.

10. Protection of Human Subjects

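### Section 9.5 calculates precision as if respondents were independent, although they come from about 10 centres, so the stated precision is optimistic to the extent that answers cluster by centre

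*Protocol*

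**What the plan says.** Section 9.5 justifies the study size by precision alone. Table 2 gives 95% limits for receipt at 60, 70, 80 and 90%, "according to a range of correct response to the primary endpoint question of receipt using the Clopper-Pearson method". The text picks out the precision "for correct responses of 60% and 90%, respectively, for the primary endpoint question of receipt". Table 3 covers the knowledge score; its rows are set by "Expected SD around the mean score of correct responses", with values of 0.5 to 3.5, and its title again names Clopper-Pearson. The visible columns of both tables hold only the sample size, the response rate or standard deviation, and the resulting precision. None holds a number of centres, an ICC or a design effect.

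Respondents are recruited through centres. The Study Design Schema states: "A total of approximately 10 haematology centers will be selected to participate in the study". Section 9.2.2 has each centre include patients and caregivers consecutively up to a target for that centre, and allows further hospitals if recruitment is slow.

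Section 9.9 says: "The size of the study populations will allow an acceptable level of precision", qualified by the rarity of the disease and stated separately for patients and caregivers. Its list of limitations does not mention correlation within centres.

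**The concern.** The Clopper-Pearson interval is an exact binomial interval and assumes that each respondent's answer is independent of the others. A patient cannot report receiving a brochure that the centre did not hand out, so answers on receipt from one centre may well agree more than answers from different centres. Section 9.9 itself treats the centre as the channel for information: "The conduct of the survey may cause centres to provide more information to patients and caregivers". With about 10 centres, adding respondents within a centre then yields less information than the tables credit.

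The precision is what the protocol offers in support of its study size. Sections 4 and 8.2 also read the measures as successful if a majority of participants confirm receipt and have the knowledge. If receipt clusters by centre, an interval that appears to lie above one half may not do so once centre is taken into account.

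**Working it through.** **Inputs from the protocol.** Two-sided 95% intervals, Clopper-Pearson for receipt, receipt of 60 to 90%, and knowledge standard deviations of 0.5 to 3.5 (section 9.5); about 10 centres (Study Design Schema); patients and caregivers analysed separately (section 9.7.2.4).

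**Assumed inputs.** The sample sizes and all limits in Tables 2 and 3 are blacked out, so the stated precision cannot be reproduced. I take n = 20 to 100 per group, 10 equal centres, and ICC 0.1 to 0.3.

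**Formulas.** With m = n/10 respondents per centre, the design effect is DE = 1 + (m − 1) × ICC and the effective sample size is n_eff = n/DE. The Clopper-Pearson limits are the beta quantiles B(0.025; x, n_eff − x + 1) and B(0.975; x + 1, n_eff − x), with x = p × n_eff.

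**Receipt at p = 60%:**

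| n per group | ICC | DE | n_eff | 95% limits (%) | Half-width (points) |
|---|---|---|---|---|---|
| 30 | 0 | 1.0 | 30 | 40.6–77.3 | 18.4 |
| 30 | 0.1 | 1 + 2 × 0.1 = 1.2 | 25 | 38.7–78.9 | 20.1 |
| 30 | 0.3 | 1 + 2 × 0.3 = 1.6 | 18.75 | 35.2–81.5 | 23.1 |
| 50 | 0 | 1.0 | 50 | 45.2–73.6 | 14.2 |
| 50 | 0.1 | 1 + 4 × 0.1 = 1.4 | 35.7 | 42.3–76.0 | 16.8 |
| 50 | 0.3 | 1 + 4 × 0.3 = 2.2 | 22.7 | 37.6–79.7 | 21.1 |

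**Against one half.** At 60% the lower limit is below 50% even under independence. At 80% and 90% it stays above 50% for both sample sizes and both ICC values. The row that changes is 70%:

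| n per group | Lower limit, ICC 0 | ICC 0.1 | ICC 0.3 |
|---|---|---|---|
| 30 | 50.6% | 48.5% | 44.8% |
| 50 | 55.4% | 52.4% | 47.4% |

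**Coverage of the unadjusted 95% receipt interval.** Beta-binomial simulation, 10 equal centres, 40,000 runs, range over true receipt of 60, 80 and 90%:

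| n per group | ICC 0.1 | ICC 0.3 |
|---|---|---|
| 20 | 95–98% | 93–98% |
| 30 | 94–99% | 90–97% |
| 50 | 93–94% | 85–87% |
| 100 | 86–88% | 69–74% |

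Under independence at n = 30 the simulated coverage is 96–99%. That surplus absorbs a small design effect.

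**Knowledge.** The half-width of a mean is about 1.96 × SD/√n and grows by √DE. With SD 2.5 and n = 50 it is 1.96 × 2.5/√50 = 0.69 under independence, 0.69 × √1.4 = 0.82 at ICC 0.1, and 0.69 × √2.2 = 1.03 at ICC 0.3. An interval for a mean has no built-in conservatism to offset this. The Clopper-Pearson method named in the title of Table 3 does not apply to a mean score.

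**The case against.** The strongest reply is that no shortfall has been demonstrated. The sample size is blacked out, the protocol gives no ICC, and equal centres are an assumption. Clopper-Pearson is conservative, and at 20 to 30 per group with ICC 0.1 the simulated coverage remains at about 94% or more. Further centres may be added, which would lower the number per centre and so the design effect. This stands: a reader might infer that the intervals are shown to be too narrow, and the document does not support that.

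The mechanism is also inferred. The section 9.9 sentence about centres giving more information concerns a Hawthorne effect, and no rule in the protocol states that centres distribute the materials. Clustering of receipt is plausible, not established.

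The protocol is descriptive and tests no hypothesis. It attaches no confidence-limit rule to its majority criterion, and it already admits in section 9.5 that its intervals are wider than usual. That admission rests on rarity and feasibility, however, and gives no hint that the tabulated widths assume independence.

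The interval method for the final analysis may be set in the statistical analysis plan, which is not shown. Section 9.7 fixes no unclustered method, so it is not at fault. This does not answer the point on section 9.5, where the planning precision is already fixed and used to support the study size.

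A reader might also infer from section 9.7.2.5.1 that patients and caregivers are pooled in an overall figure, counting one set of materials twice. Section 9.7.2.4 analyses the two groups separately, and the word overall there contrasts with the subgroups, so that reading is not supported.

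**Conclusion.** The point holds for the planning precision. Tables 2 and 3 assume independent respondents, the design draws them from about 10 centres, and no visible text allows for the difference. For any positive ICC with more than one respondent per centre, the true precision is worse than such a calculation gives.

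How much worse depends on figures that the document does not show. For ICC 0.1 to 0.3 and 60% receipt, the half-width grows by 1.7 to 4.7 points at 30 per group (20.1 − 18.4; 23.1 − 18.4) and by 2.6 to 6.9 points at 50 (16.8 − 14.2; 21.1 − 14.2). The effect on receipt coverage is small at 20 to 30 per group with a low ICC and material at about 50 per group or with a high ICC. The reading of a majority is sensitive mainly near 70% receipt. This is a correction that should be made; it does not invalidate the survey.

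**What to change.** 1. In section 9.5, restate Tables 2 and 3 with the design effect 1 + (m − 1) × ICC for about 10 centres over a stated ICC range, for example 0.1 to 0.3. In Table 3, name a method suited to a mean.
2. In section 9.9, amend the precision statement to match, and list clustering by centre among the limitations.
3. Report receipt intervals that allow for centre, with a simple display of receipt by centre. With about 10 centres of a few respondents each, an estimated ICC will be unstable, so an effective sample size over the stated ICC range is a workable choice. The detail can go in the statistical analysis plan. The subgroups in section 9.7.2.5.1 (country, education, materials read or not) would not by themselves reveal a centre that does not hand out the materials.

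The cost is a slightly less favourable stated precision and a little analysis work. No more patients or centres are needed.

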9.6 Data Management

A data management plan (DMP) will be written to guide of all aspects of data handling. It will include all data forms and annotations, testing documentation and summaries, database documentation, merging of datasets and transfer of files into SAS for statistical analysis. All data collected during the survey will be held confidentially.

As discussed in Section 10.3 the identities of patients taking part in the survey will be controlled by the use of unique identification codes. These source ID numbers will be held securely, and these data will be used solely for the purpose of identifying whether the patient/caregiver has completed the survey.

9.6.1 Obtaining Data Files

Completed paper forms will be forwarded to CCI by the site staff for data entry. CCI data entry staff will enter the paper questionnaire into a database for analysis.

A database will be created and tested before data entry, two copies of the same database will be prepared. Double data entry will be performed and databases compared until no discrepancies are found. The final database will be transferred to SAS for analysis.

9.6.2 Linking Data Files

In addition to the paper questionnaire, an identification log will be completed by the study site. As described in Section 10.3, a unique code will be assigned to each patient and caregiver, which will be used to link the paper questionnaire with the identification log

which will be kept by the investigator and site staff. The feasibility and recruitment process will be registered in an excel database and managed by the study operations staff involved in the recruitment of centres.

9.6.3 Review and Verification of Data Quality

As this study is collecting data from patients and caregivers through a survey questionnaire, it is not planned to generate queries in the study. Double data entry will be performed to minimize potential errors.

9.7 Data Analysis

Statistical analyses will be mainly descriptive. A detailed statistical analysis plan (SAP) will be developed before final database lock and will include methods of analysis and presentation and table shells. All analyses will be performed using SAS 9.3 (or higher) statistical software (SAS, Cary, North Carolina, USA).

9.7.1 Planned Analyses

9.7.1.1 Primary Analysis

The primary analysis will be performed at one point in time, once the database is locked for analysis, and will address all the study objectives as described below.

9.7.2 Planned Method of Analysis

The study endpoints will be addressed using descriptive statistics.

9.7.2.1 General Considerations

Categorical data will be summarized by counts and percentages. Continuous data will be summarized using number, mean, standard deviation (SD), median, quartiles, minimum and maximum and in the case of non-normally distributed data, median, range and interquartile range. Corresponding 95% confidence intervals will be reported as appropriate. No adjustment will be made for multiple comparisons or for multiple analyses. All figures will be presented to three decimal places.

The statistical analysis will include a summary of the study conduct, a descriptive analysis and the analysis of the objectives. Site characteristics (type of centre i.e. academic/non-academic) will be described.

Patient/caregiver representativeness: Patients/caregivers approached at the sites for enrollment, whose demographic profile information has been collected in the patient log (age and gender), will be divided into:

- Eligible patients/caregivers who agree to participate in the study

- Eligible patients/caregivers who refuse to participate in the study

9.7.2.2 Missing or Incomplete Data and Lost to Follow-up

Responses to questions in the patient/caregiver questionnaire may be missing or illegible.

They will be dealt with in two ways:

- In the primary analysis, missing/illegible data will be ignored.
- As a sensitivity analysis, a conservative assumption will be made in which missing values will be considered as incorrect or worst responses.

For questions without a correct or best response, missing/illegible data will be ignored in the analysis.

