Haemato-oncologists/nurses in participating centres will include patients and their associated caregivers who fulfil all the selection criteria listed below in a consecutive manner according to the date of initiation of treatment with Blincyto until reaching the target number of patients/caregivers to be recruited per centre. Caregivers can be a spouse, family member, friend or professional helper who has helped with Blincyto treatment. The consecutive selection of patients and caregivers at each site is designed to minimise selection bias and to allow for the study results to be generalisable to the entire population of Blincyto treated patients. To assess generalizability of the data, sites will be asked to keep a log of anonymized demographic profiles (age and sex) of patients administered Blincyto, and their caregivers.

CCI

[figure not shown]
Figure 1. Illustration of sampling strategy

Patients/caregivers who agree to participate in the study with informed consent will be asked to complete a paper questionnaire after discharge from hospital **preferably** when they return to clinic for a bag change or monitoring (Figure 2). Both the patient and the caregiver will be invited to participate in the survey: **however, one can participate without the participation of the other**. If the patient is not well enough to complete the questionnaire on returning to clinic after hospital discharge on Blincyto, the patient will be asked again at the next visit. If a caregiver is not available at a visit, they will be asked at the next available visit to participate. Only one caregiver per patient will be recruited.

Appropriate measures will be adopted to ensure physicians do not influence patient/caregiver's choices (e.g. patients and caregivers will place their completed questionnaires in a sealed envelope).

Figure 2. Illustration of treatment characteristics and questionnaire administration

Note: Patients/Caregivers will complete the questionnaire based upon their first exposure to Blincyto at home. However, the questionnaire may be administered subsequent to blincyto cycle 1

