9.7.2.3.1 Description of Study Enrollment

The study populations as identified in the recruitment process will be described. Recruitment rates and a description of the number of patients/caregivers in the study and analysis populations will be provided.

Analysis sets: As shown in [Figure 3](#), datasets for analysis will be further described in the SAP and will include:

- Study population: All adult patients with R/R Ph- B-precursor ALL initiating Blincyto (or their caregivers).
- Eligible Set: All patients/caregivers who fulfill the eligibility criteria.
- Enrolled Set: All eligible patients/caregivers who agree to participate in the study.
- Full Analysis Set: All patients/caregivers who complete the questionnaire of their corresponding survey and have valid responses to allow for the assessment of the primary objective.
- Safety Set: This is the same as the Enrolled Set.

Figure 3. Study Population and Datasets flow-chart

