9.9 Limitations of the Research Methods

The number of patients willing/able to participate in the survey may be lower than expected because of the severity of the condition and complications during **treatment with Blincyto**: neutropenic fever, infections, and neurological side effects. Responses by caregivers may be anticipated to be different (better?) than patients, as they are often more attentive of the details of the management of their family member or friend, especially in these patients, many of whom will experience side effects and be quite ill during their therapy with Blincyto. This will be assessed by analyzing patients and caregivers separately.

The questionnaire has been designed to facilitate completion by the patient/caregiver on paper. For this reason, some of the questions that address secondary endpoints refer to 'educational materials' in general (e.g. understanding, usage) and do not allow drawing conclusions for each type of material i.e. card and brochure. However, most of the questions apply only to the brochure and some of the questions apply only to the card.

The survey will exclude patients (caregivers of patients) who have only received Blincyto in hospital. This restriction will result in a more meaningful assessment as only patients/caregivers who have the chance to have used the materials will be included; materials are mainly used in the outpatient setting where MEs are more likely to occur. In

addition, the completion of the survey by the patient/caregiver will be restricted to the period after discharged from hospital and ambulatory treatment at home. This time interval is expected to allow sufficient time for the provision and usage of the materials, and the occurrence of MEs (if any), without hindering recruitment.

The survey may be affected by selection bias within centres and non-participation. Consecutive recruitment based on treatment initiation during the study period will be used to avoid selection bias. A log of patients initiating Blincyto during the study period will be kept to check this recruitment process.

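### The worst-case sensitivity analysis covers item non-response only, so nothing in the plan bounds receipt among enrolled people without a usable questionnaire or among eligible refusers

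*Protocol*

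**What the plan says.** Protocol 9.7.2.2 sets its own scope in its opening sentence: "Responses to questions in the patient/caregiver questionnaire may be missing or illegible". Two treatments follow. For the main result, "In the primary analysis, missing/illegible data will be ignored". For the sensitivity analysis, "a conservative assumption will be made in which missing values will be considered as incorrect or worst responses".

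Section 9.7.2.3.1 defines a chain of sets. It includes "Eligible Set: All patients/caregivers who fulfill the eligibility criteria", then an Enrolled Set of those who agree to take part, and a Full Analysis Set of "All patients/caregivers who complete the questionnaire of their corresponding survey and have valid responses to allow for the assessment of the primary objective". Section 9.7.2.4 reports the endpoints on people with valid responses to all relevant questions.

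On people who do not take part, 9.7.2.1 uses the site log of age and gender to separate those who agree from "Eligible patients/caregivers who refuse to participate in the study". Section 9.7.2.3.1 adds recruitment rates and the numbers in each population. Section 9.9 warns that "The number of patients willing/able to participate in the survey may be lower than expected because of the severity of the condition" and lists non-participation as a possible source of bias.

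On the target of inference, section 8 asks whether the safety information reached the target population. Section 9.2.2 says that consecutive selection is meant "to allow for the study results to be generalisable to the entire population of Blincyto treated patients". The success statement in 8.2 (also in the Abstract) is narrower: it refers to a majority of those taking part, read alongside response rate and recruitment.

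**The concern.** There are two gaps, one inside the questionnaire data and one outside.

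Inside, the worst-case rule and the Full Analysis Set pull against each other. If a valid receipt answer is needed to enter the Full Analysis Set, a person who left it blank has gone before the blank can be scored as not received. The sensitivity analysis of receipt could then reproduce the primary result exactly and be read as reassurance.

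Outside, people who agree but return nothing usable, and eligible people who decline, contribute to no receipt figure. The log comparison says whether they differ in age and gender, not whether they had the brochure or card. A report could therefore show a majority that holds up under an analysis called conservative, next to a research question about the whole target population, without any statement of how far non-participation could move the answer.

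**Working it through.** **Inputs from the protocol.** Planning receipt values are 60% to 90% (9.5, Table 2). Section 9.5 speaks of correct responses to the receipt question, so receipt has a best answer and the worst-case rule is meant to apply to it. Majority is read as more than 50%. The planned sample size and the Table 2 limits are redacted, so there is no stated figure to reproduce.

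**Assumed.** Participation rate *q* among eligible people approached (no rate is stated) and share *m* of blank receipt answers.

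**Formulas**, with *r* the receipt proportion among participants:

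- Item rule only: *r*(1 − *m*).
- Worst case over those approached, all non-participants counted as not received: *q r*.
- Best case: *q r* + (1 − *q*).
- Participation above which a majority is guaranteed: 0.5 / *r*.
- Tipping point, the receipt among non-participants at or below which the overall majority is lost: (0.5 − *q r*) / (1 − *q*).

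| *r* | Item rule, *m* = 5% | Item rule, *m* = 10% | Worst case, *q* = 80% | *q* = 60% | *q* = 50% | Guaranteed above |
|---|---|---|---|---|---|---|
| 60% | 57.0% | 54% | 48% | 36% | 30% | 83.3% |
| 70% | 66.5% | 63% | 56% | 42% | 35% | 71.4% |
| 80% | 76.0% | 72% | 64% | 48% | 40% | 62.5% |
| 90% | 85.5% | 81% | 72% | 54% | 45% | 55.6% |

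With 5% or 10% blanks the item rule leaves every majority in place. The wider bound may or may not do so, depending on participation.

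**Tipping points:**

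- *r* = 60%, *q* = 60%: (0.50 − 0.36) / 0.40 = 35%.
- *r* = 80%, *q* = 60%: (0.50 − 0.48) / 0.40 = 5%.
- *r* = 90%, *q* = 50%: (0.50 − 0.45) / 0.50 = 10%.

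**Example with assumed counts.** 50 eligible people are approached, 30 enrol, 2 leave receipt blank and 23 report receipt.

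- Primary: 23/28 = 82.1%.
- Worst case if the Full Analysis Set has already dropped the 2 blanks: again 23/28 = 82.1%, so the sensitivity analysis changes nothing.
- Worst case on the Enrolled Set: 23/30 = 76.7% (exact 95% CI 57.7% to 90.1%).
- Worst case over those approached: 23/50 = 46.0% (31.8% to 60.7%).
- Best case over those approached: (23 + 2 + 20)/50 = 90.0%.
- Tipping point: a majority of 50 needs 26, so 3 of the 22 people with unknown receipt (13.6%) would have to have received the materials.

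**Counter-example.** 50 approached, 40 enrol, 2 blanks, 30 report receipt. Primary 30/38 = 78.9%; Enrolled Set worst case 30/40 = 75.0%; worst case over those approached 30/50 = 60.0%. The majority holds throughout.

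**The case against.** The strongest reply is that 9.7.2.2 states its scope openly, and conservative there describes how blanks are scored, not a claim about non-participation. Analyses on wider sets are ordinary SAP content; 9.7 and 9.7.2.3.1 both defer detail to a SAP, which is not among the documents. It stands that a missing bound alone would not be an error in a protocol. What remains is that the protocol itself fixes the sensitivity rule and a Full Analysis Set that may prevent the rule from acting on receipt.

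Four stronger readings are tempting, and the documents do not support them.

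- **That the success criterion fails once non-participants are counted.** Section 8.2 defines the majority among participants, so it cannot fail that way. Only the wider question in sections 8 and 9.2.2 is left open.
- **That the protocol expects non-participation to be the larger loss.** Section 9.9 says that numbers may be low and that item non-response should be minimised. It does not rank the two.
- **That non-participants probably lacked the materials.** Nothing links illness during treatment to lower receipt. Section 7.1 obliges the marketing authorisation holder to ensure provision, and the brochure in Appendix F asks to be read before treatment, so intended receipt comes before most illness that would prevent participation. Counting all non-participants as not received is an extreme bound.
- **That a worst case above 50% should be required to call the result robust.** At 60% receipt this would need more than 83% participation in severely ill patients. It is a debatable choice, and nothing in the protocol calls for it.

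The existing safeguards also count. Patients too unwell to answer and caregivers who are absent are asked again at a later visit (9.2.2), and response rate and recruitment inform interpretation (8.2). They reduce or describe non-participation but put no limit on its effect on receipt.

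Finally, recruitment at a centre stops at its target number (9.2.2), so the Eligible Set may include people never approached. It is a poor denominator for a bound.

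**Conclusion.** The point holds in a limited form. The sensitivity analysis addresses item non-response only, may not reach a blank receipt answer at all because of how the Full Analysis Set is defined, and leaves enrolled people without a usable questionnaire and eligible refusers outside every receipt analysis.

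The size depends on a participation rate that the protocol does not give. Across the planning range, a majority among those approached is guaranteed only above 55.6% participation (at 90% receipt) to 83.3% (at 60% receipt). Below those rates the majority is not refuted. Whether it is lost depends on receipt among non-participants, with tipping points from 5% to 35% in the three cases worked above. The calculation assumes that majority means more than 50% and that those approached stand for the target population.

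This is an inexpensive improvement that limits what a respondent majority can be said to show. It does not invalidate the design.

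**What to change.** In 9.7.2.2:

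- **(a)** State that conservative refers to item non-response. Run the receipt worst case on the Enrolled Set, so that blank receipt answers and unusable questionnaires count as not received, and reconcile this with the Full Analysis Set definition in 9.7.2.3.1.
- **(b)** Beside the response rate, show worst-case receipt, best-case receipt and the tipping-point receipt among non-participants. Use as denominator the eligible people actually approached, from the log described in 9.7.2.1. Do this for patients and caregivers separately.
- **(c)** Where the worst case does not exceed 50%, report the finding as a majority of respondents. Attach no pass/fail label for robustness.

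The counts come from the log and the population numbers already planned, so no new data collection is needed. The cost is a few table rows, plus bounds that will be wide if participation is low.
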